7.0 PATIENT DISPOSITION

The number of patients in 3 of the study populations (Randomized, Safety, and ITT) will be summarized by treatment group and study center; the Screened Population will be summarized overall only by study center.

Screen-failure patients (i.e., patients screened but not randomized) and the associated reasons for failure to randomize will be tabulated overall for the Screened Population. The number and percentage of patients who complete the double-blind treatment period and of patients who prematurely discontinue during the same period will be presented for each treatment group and pooled across treatment groups for the Safety Population. The number and percentage of patients who enter the down-taper period and of patients who complete the down-taper period will be presented for each treatment group and pooled across treatment groups for the Safety Population.

The reasons for premature discontinuation from the double-blind treatment period as recorded on the disposition pages of the electronic case report forms will be summarized (number and percentage) by treatment group for the Safety Population. Percentage of premature discontinuations will be compared overall and for each discontinuation reason between treatment groups using Fisher's exact test. All patients who prematurely discontinue during the double-blind treatment period will be listed by discontinuation reason for the Safety Population.

8.0

DEMOGRAPHICS AND OTHER BASELINE CHARACTERISTICS

Demographic parameters (age, sex, race, ethnicity) and other baseline characteristics (weight, height, body mass index) will be summarized descriptively by treatment group for the Safety and ITT populations, respectively. Baseline efficacy variables will be summarized by treatment group for the ITT Population.

Continuous variables will be summarized by number of patients and mean, SD, median, minimum, and maximum values. Categorical variables will be summarized by number and percentage of patients.

Comparability between treatment groups will be tested using a 2-way analysis-of-variance (ANOVA) model with treatment group and study center as the factors for continuous variables and a Cochran-Mantel-Haenszel (CMH) test, controlling for study center, for categorical variables.

Medical and surgical history/physical findings will be classified by system organ class and preferred term using the *Medical Dictionary for Regulatory Activities*, version 17.0 or newer. The number and percentage of patients with abnormalities in medical and surgical histories in each system organ class and preferred term will be summarized by treatment group for the Safety Population. Psychiatric history of major depressive disorder, other psychiatric history, prior treatment with psychotropic medication, and nondrug psychiatric treatment history will also be summarized by treatment group for the Safety Population.

The *World Health Organization Drug Dictionary*, version March 2014 or newer, will be used to classify prior and concomitant medications by therapeutic class and drug name.

Prior medication is defined as any recorded medication taken before the date of the first dose of double-blind investigational product. *Concomitant medication* is defined as any medication taken on or after the date of the first dose of double-blind investigational product.

Both prior and concomitant medications use will be coded by drug name and therapeutic class. The use of prior and concomitant medications will be summarized by the number and percentage of patients receiving each drug within each therapeutic class in each treatment group for the Safety Population. If a patient took a specific medication multiple times or took multiple medications within a specific therapeutic class, that patient would be counted only once for the coded drug name or therapeutic class.

Summaries for concomitant medication use will be presented for the double-blind treatment period and the down-taper period, separately. Any concomitant medications taken after the date of the last dose of double-blind investigational product in the study will not be presented in the summary tables but will be included in the patient data listings.

9.0 EXTENT OF EXPOSURE AND TREATMENT COMPLIANCE

9.1 EXTENT OF EXPOSURE

Exposure to double-blind investigational product for the Safety Population during the double-blind treatment period will be summarized in terms of treatment duration, calculated as the number of days from the date of the first dose of double-blind investigational product to the date of the last dose of double-blind investigational product during the double-blind treatment period, inclusive. Descriptive statistics (number of patients, mean, SD, median, minimum, and maximum) will be presented by treatment group. The number and percentage of patients will be presented for specific intervals of exposure by treatment group.

Patient-years, defined as total exposure to double-blind investigational product in years (excluding the down-taper period), will be summarized by treatment group for the Safety Population.

In addition, weekly and overall mean daily dose, overall modal daily dose, and final daily dose of investigational product during the double-blind treatment period will be summarized by treatment group for the Safety Population.

9.2 MEASUREMENT OF TREATMENT COMPLIANCE

[REDACTED]

10.0 **EFFICACY ANALYSES**

The efficacy analyses will be based on the ITT Population. *Baseline* for efficacy is defined as the last nonmissing efficacy assessment (at or prior to Visit 2) before the first dose of double-blind investigational product. All statistical tests will be 2-sided hypothesis tests performed at the 5% level of significance for main effects. All confidence intervals will be 2-sided 95% confidence intervals, unless stated otherwise.

For efficacy analyses in which study center is a factor, a small center will be defined as a center with fewer than 2 patients in any treatment group in the ITT Population. Small centers will be pooled to form pseudo-centers so that each treatment group includes at least 2 ITT patients within the center. Pooling will be done (within each country first) using the following algorithm:

Based on the number of ITT patients, small centers will be ordered from the largest to the smallest, and centers of the same size will be ordered from the largest center code to the smallest center code. The pooling process starts with the largest small center from the top, which will be pooled with the smallest from the bottom until a non-small pseudo center is formed. The process will be repeated using the small centers left out after the first pass. If any centers are left out at the end of the process, they will be pooled with the smallest pseudo center. If there is more than 1 smallest pseudo center, the pseudo center with the smallest center code will be selected. In case that the pseudo center formed by pooling all small centers is still a small center, it will be pooled with the smallest non-small center. If there is more than 1 smallest non-small center, the one with the smallest center code will be selected.

These pseudo-centers will be used for all efficacy analyses when the model is adjusted for study center.

By-visit analyses based on the mixed-effects model for repeated measures (MMRM) using the observed case (OC) approach will be performed for all continuous efficacy parameters with multiple post-baseline measurements.

In addition, by-visit analyses using the last-observation-carried-forward (LOCF) approach will be presented for all efficacy parameters. For the LOCF approach, only the postbaseline total score of a parameter will be imputed; individual item scores will not be carried forward to derive the total score. Baseline total score will be carried forward only for the intermittent missing scores immediately after baseline. If all the postbaseline values are missing, the baseline value will not be carried forward.

10.1 PRIMARY EFFICACY PARAMETER

The primary efficacy parameter is the change from baseline to Week 8 in CDRS-R total score. The primary analysis for comparing vilazodone vs placebo will be performed using an MMRM with treatment group, pooled study center, visit, and treatment-group-by-visit interaction as the fixed effects and the baseline value and baseline-value-by-visit interaction as the covariates. An unstructured covariance matrix will be used to model the covariance of within-patient scores. The Kenward-Roger approximation (Kenward and Roger, 1997) will be used to estimate denominator degrees of freedom. This analysis will only use the observed cases of postbaseline scores without imputation of missing values.

To control the overall type I error rate for the multiple comparisons across the primary and the secondary hypotheses, a fixed sequence procedure will be applied. Details are provided in Section [10.2](#).

In addition, two sensitivity analyses, LOCF and pattern-mixture model approaches, will be performed on the primary efficacy parameter. The LOCF approach is based on an analysis-of-covariance (ANCOVA) model including treatment group and pooled study center as factors and baseline CDRS-R total score as a covariate. Another sensitivity analysis using a pattern-mixture model approach based on non-future dependent missing value restrictions (Kenward et al., 2003) will be performed to assess the robustness of the primary MMRM results to the possible violation of the missing-at-random assumption. The details of this sensitivity analysis are as follows:

The pattern for the pattern-mixture model will be defined by the patient's last visit with an observed value. The observed CDRS-R total score at a visit is assumed to have a linear relationship with the patient's prior measurements. The missing values will be imputed under the assumption that the distribution of the missing observations differs from that of the observed only by a shift parameter value Δ . The dataset with missing values imputed will be analyzed using an ANCOVA model with treatment group and pooled study center as factors and baseline CDRS-R total score as a covariate for between-treatment group comparisons at Week 8. The imputation of missing values and the analysis will be performed multiple times and the inference of this sensitivity analysis will be based on the combined estimates using the standard multiple imputation technique. The range of values for the shift parameter Δ is selected as 0 to 6 based on experience with historical data.

More details of the proposed pattern-mixture model approach (e.g., the models for the pattern-specific identifiable densities and the unidentified conditional distributions, the shift parameter Δ , and the multiple imputation algorithm) are provided in Appendix I to this SAP.

To examine the consistency of the primary efficacy results across study centers, the treatment differences versus placebo treatment groups (mean \pm SE) in the change from baseline to Week 8 in CDRS-R total score will be graphed by pooled study center.

The comparison of fluoxetine vs. placebo will be performed to assess study assay sensitivity.

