Note that the two distributions only differ by a shift (Δ) parameter. When $\Delta = 0$, the missing value y_s in Pattern $s - 1$ is imputed based on the distribution of all observed data up to Visit s , as a result, leading to missing at random (MAR) missingness. When $\Delta \neq 0$, (8) will introduce a scenario of MNAR. The similar idea was also presented in the recent publication “The Prevention and Treatment of Missing Data in Clinical Trials” by the National Academies Press. The selection of the plausible values for the shift parameter (Δ) is discussed in Section 3 of this appendix.

Note that per recommendation in Wang and Daniels (2011), only the observed data within pattern is assumed to be multivariate normal. The observed data distribution can be expressed in terms of the marginal distribution of baseline measurement and the conditional distributions of postbaseline measurements given earlier measurements. Assuming that these distributions are normal, the linear regression of each observation on prior observations will yield least-squares estimates of model parameters that can be utilized for independent posterior draws of model parameters for observed data. Multiple imputation approach will be used to estimate the overall mean at the final time point.

2. Imputation Procedure

All the missing data will be imputed to create complete datasets, then statistical analysis can be performed using appropriate techniques such as ANCOVA. The imputation can accommodate MNAR missing data mechanisms, based on the theory discussed in the previous section.

The model parameters for each dropout pattern, i.e., the mean, variance and proportions of observations in each pattern, are drawn from their posterior distributions prior to the imputation of missing data for a single imputation.

The details of imputation within a pattern, say Pattern t , are as the following:

Step 1. Impute the first missing value y_{t+1} for each patient in Pattern t ($t = 1, \dots, T - 1$):

- a. Compute estimates of mixture probabilities $\lambda_{s-1,j}$ in (7) with $s = t+1$ given the posterior draw of proportions of observations in each pattern and the posterior draw of regression parameters for the observed data.
- b. Draw a random integer from $\{s, \dots, T\}$ to index a component distribution on the right hand side of (6), using mixture probabilities obtained in a). Draw y_{t+1}^* from the identified component normal distribution. Impute the missing y_{t+1} as

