$$\tilde{y}_{t+1} = y_{t+1}^* + \Delta.$$

Step 2. Impute the rest of the missing values of $y_{t+2}, y_{t+3}, \dots, y_T$ for patients in Pattern t :

Starting with imputation for y_{t+2} , first, similar to Step 1, draw y_{t+2}^* from the normal mixture (6) based on the observed y_1, \dots, y_t and the already imputed \tilde{y}_{t+1} for the patient.

Then the missing y_{t+2} is imputed as $\tilde{y}_{t+2} = y_{t+2}^* + \Delta$ with probability δ_{t+1} and as $\tilde{y}_{t+2} = y_{t+2}^*$ with probability $1 - \delta_{t+1}$, where the mixture probability $\delta_{t+1} = \omega_{t+1,t+1}$ is obtained from (4) given the posterior draw of proportions of observations in each pattern and the posterior draw of regression parameters for the observed data.

Missing values of y_{t+3} through y_T can be imputed similarly as y_{t+2} .

To summarize, the imputations of y_{t+1} through y_T is done recursively within each Pattern t (for all $t = 1, \dots, T - 1$) to create a complete dataset after imputation is done for all patterns with missing values.

The above imputation procedure is applied to all subjects in each missing data pattern to create a single imputed data set. Repeating the process of drawing parameters from the posterior distribution and imputing missing data given the posterior draw m times will yield m imputed data sets. The observed or imputed values at the final data point are averaged to obtain the overall mean estimate for each imputed data set, and the multiple imputation estimate is obtained by averaging the estimates across m imputations.

In this sensitivity analysis, m is set to equal to 20. The value of m is discussed in the context of imputation efficiency in standard multiple imputation theory (Rubin, 1987, p. 114), and $m = 20$ would provide at least 96% of relative efficiency as compared with using a large number of imputations (SAS/STAT User's Guide, p. 3796).

3. Determination of the Shift Parameter Values

The common shift parameter Δ is the difference between the mean of y_{t+1} among those who drop out at Visit t and those who remain beyond Visit t ($1 \leq t \leq T-1$). The exact value of Δ is unknown and can't be estimated from data because of missingness. The magnitude of Δ depends on the medical aspects of the trial. Using relevant historical data, one may select Δ as a proportion of the sample standard deviation or a proportion of observed treatment efficacy.

References:

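### The pattern-mixture sensitivity analysis uses one shift Δ for all arms, so varying Δ from 0 to 6 does not test vilazodone dropouts alone doing worse than missing-at-random predicts

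*SAP*

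**What the plan says.** SAP 10.1 plans two sensitivity analyses of the primary comparison, LOCF and a pattern-mixture model. The second is there to check whether the MMRM result survives a departure from missing at random (MAR). It imputes missing scores assuming that "the distribution of the missing observations differs from that of the observed only by a shift parameter value" Δ, and the range of Δ "is selected as 0 to 6 based on experience with historical data". On the patterns, SAP 10.1 states: "The pattern for the pattern-mixture model will be defined by the patient's last visit with an observed value". Protocol 9.7.5.1 describes the same method.

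Appendix I gives the details. Section 3 calls Δ common. Equations (1) to (8) are indexed by visit and dropout pattern, never by treatment. On the imputation models, section 1 says that "the linear regression of each observation on prior observations will yield least-squares estimates of model parameters". At Δ = 0 a first missing value "is imputed based on the distribution of all observed data up to Visit" s, "as a result, leading to missing at random (MAR) missingness"; a nonzero Δ "will introduce a scenario of MNAR". Section 2 adds: "The above imputation procedure is applied to all subjects in each missing data pattern to create a single imputed data set". Treatment is named only in the Week 8 ANCOVA run on the completed data. The primary MMRM, by contrast, contains treatment group and its interaction with visit.

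**The concern.** A shift added to dropouts in every arm lowers the apparent improvement in every arm. If the arms lose similar numbers of patients at similar times, the between-arm difference stays where it was, whatever the value of Δ. A reader shown stable results from Δ = 0 to 6 would take them as evidence of robustness, although they are nearly guaranteed by the construction.

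The untested case is plausible. Patients who need a new treatment are discontinued from the study (Protocol 9.4.10), so their later course is not seen, and only an active arm has a drug effect to lose. The Early Termination visit (Protocol 9.3.3) should record worsening up to exit, so the issue is the unobserved time after it.

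There is also an ambiguity. If the imputation regressions are fitted without arm, imputed vilazodone scores are pulled toward the other arms even at Δ = 0. That is not the MAR assumption of the MMRM, which conditions on arm.

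**Working it through.** Differences are points of advantage to vilazodone; a negative change goes against vilazodone.

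**Inputs from SAP 14.0 and Appendix I.** 188/188/94 patients, SD 12.43, correlation 0.7, dropout 17% (one figure, not by arm), m = 20. Visits 3 to 8 give six post-baseline visits (Protocol 9.7.2).

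**Assumptions not in the documents.** The SAP gives 0.7 without a structure, so both exchangeable and AR(1) are shown. The last visit before dropout is weighted over the first five visits as even (1:1:1:1:1), early (5:4:3:2:1) or late (1:2:3:4:5). The drug effect builds linearly.

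**The plan's own figure.** A difference of 4 with SD 11.1 needs 139 per arm with complete data. With even dropout the Week 8 variance inflates by 1.083 (exchangeable) or 1.163 (AR(1)), and power at 160 per arm is 87.2% or 84.8% against the stated 85%. Both are close, so the stated power does not settle the structure. At 188 per arm, SE = 12.43 × √(2 × 1.083/188) = 1.33, or 1.38 with 1.163. The simulated multiple-imputation SEs were 1.34 to 1.39, and these are used below.

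**How much of Δ reaches Week 8.** Let k be the share of Δ surviving to Week 8 per dropout. The first missing visit is shifted by Δ. Each later visit gets Δ with probability δ, plus the regression on the values already imputed. For a patient last seen at the fourth of the six visits:
- δ = 0.034/(0.034 + 0.83) = 0.039.
- Exchangeable, baseline also correlated 0.7: k = 0.7/(1 + 5 × 0.7) + 0.039 = 0.195.
- AR(1): k = 0.7 + 0.039 = 0.739.

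Averaged over last visits (products from unrounded k):

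| Structure | k: even / early / late | Vilazodone-only Δ = 6: −0.17 × 6 × k |
|---|---|---|
| Exchangeable, baseline uncorrelated with change | 0.46 / 0.38 / 0.54 | −0.47 / −0.39 / −0.55 |
| Exchangeable, baseline also 0.7 | 0.41 / 0.31 / 0.51 | −0.42 / −0.31 / −0.52 |
| AR(1) | 0.61 / 0.47 / 0.74 | −0.62 / −0.48 / −0.76 |

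**Common Δ.** Change in the difference = Δ × (p_pbo × k_pbo − p_vlz × k_vlz), where p is the dropout proportion.
- Equal p and k: 0. Simulation of Appendix I Steps 1 and 2 gave −0.03 to +0.03 at Δ = 6 (Monte Carlo SE 0.015 to 0.021), with arms pooled or separate. A larger exchangeable run with by-arm imputation gave about 0.00, and +0.05 when dropout depended on the last score.
- Dropout of 14% in one arm and 20% in the other (assumed): about 0.2 in favour of the arm with fewer dropouts.
- 17% in both arms, but vilazodone leaving after the first two visits and placebo after the fourth or fifth: 0.29 to 0.50 in favour of vilazodone. Similar dropout must therefore mean similar timing too.

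**Pooled regressions at Δ = 0.** With even dropout a true 4 became 3.59 (exchangeable) or 3.48 (AR(1)), a loss of 0.41 to 0.52. The larger exchangeable run over even, early, late and outcome-dependent dropout gave losses of 0.43 to 0.52. With by-arm imputation there was essentially no loss.

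**LOCF.** Even dropout: 0.17 × 4 × (1 − 3/6) = 0.34 against vilazodone. The other timings gave about 0.3 to 0.4.

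**Tipping point, vilazodone-only.** Δ = (difference − 1.966 × SE)/(0.17 × k), over the k values in the table and SE 1.34 to 1.39.
- Difference 3 (p = 0.026 to 0.032): 2.9 to 7.0 exchangeable, 2.1 to 4.5 AR(1). Lowest value: (3 − 1.966 × 1.39)/(0.17 × 0.74) = 2.1.
- Difference 4: 13.7 to 26.3 exchangeable, about 10 to 17 AR(1).
- Bound if every dropout left just before Week 8 (k = 1): 1.6 to 2.2 and 7.5 to 8.0.

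**Borderline trials.** Among simulated trials with p of 0.02 to 0.05 at Δ = 0 (true difference 3, exchangeable, by-arm imputation), 84% to 90% stayed significant under common Δ = 6, against 4% to 22% under vilazodone-only Δ = 6.

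**The case against.** - **The plan already stresses vilazodone.** A reader might infer that vilazodone dropouts faring worse is not examined at all. That goes too far. If the regressions are pooled, the loss of about 0.4 to 0.5 at Δ = 0 is similar to a vilazodone-only Δ of 6 under the exchangeable structure, and a result of 3.0 falls to about 2.63 (p = 0.050 to 0.059). LOCF adds a separate penalty. What stands is that the pooled penalty is unlabelled, and that neither penalty can be varied to find where the conclusion changes.
- **The SAP does not say it pools the arms.** A reader might infer pooling from the reference to all observed data. In context it refers to all dropout patterns still observed at that visit. Appendix I uses one-sample notation throughout, so a missing arm index shows an unstated detail, not a pooled fit.
- **Cancellation holds on average.** About 10% to 16% of the borderline trials above lost significance even under common Δ = 6. That window is also selected: it held about 15% of trials at a true difference of 3 and 10% to 11% at 4.
- **The simulation simplifies Appendix I.** It fits one regression per visit rather than drawing from pattern-specific components, so small decimals should not be pressed.
- **Arm-specific shifts are partly an estimand choice.** This is fair: no passage makes outcomes after treatment stops the target. But SAP 10.1 sets out to assess violation of MAR, and a violation that differs by arm is the kind that can change the comparison.

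**Conclusion.** The point holds as a cheap improvement. Appendix I applies a common Δ and leaves open whether arm enters the imputation. With dropout similar in amount and timing, moving Δ from 0 to 6 leaves the vilazodone–placebo difference unchanged on average, so the exercise says little about robustness of the comparison that matters. This rests on similar dropout by arm, which the documents do not report, and the sizes rest on a correlation structure that they do not state.

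A reader might go on to infer that the primary result is unsafe. The documents do not support that. The primary MMRM p-value, type I error and power are untouched, and an observed difference of 4 would survive any vilazodone-only Δ within the SAP's range under every setting examined. Only a borderline result is exposed. At a difference of about 3, the tipping value often lies inside the SAP's own 0 to 6.

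**What to change.** In SAP 10.1 and Appendix I:

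1. Include treatment arm as a term in each imputation regression and in the pattern proportions, so that Δ = 0 matches the MMRM's MAR assumption. Separate regressions by arm within each dropout pattern are not practical: 188 × 0.17/5 = 6.4 vilazodone and 94 × 0.17/5 = 3.2 fluoxetine dropouts per pattern, against up to 6 parameters (intercept, baseline and four prior visits).
2. Add a run with Δ = 0 for placebo and fluoxetine dropouts and Δ = 0, 1, ..., 6 and beyond for vilazodone dropouts, until the Week 8 vilazodone–placebo comparison loses significance.
3. Report that tipping point with the mean Week 8 shift per vilazodone dropout that it implies, since only part of Δ survives to Week 8. Keep the common-Δ run as supplementary.

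The cost is SAP wording, two arm terms per regression and a few more imputation runs. No new data are needed and the primary analysis does not change. The downside is a possibly less favourable sensitivity result.
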